6.3 Subject numbering, treatment assignment, randomization

6.3.1 Subject numbering

Each subject is identified in the study by a Subject Number (Subject No.), that is assigned when the subject is first enrolled for screening and is retained as the primary identifier for the subject throughout his/her entire participation in the trial. The Subject No. consists of the Center Number (Center No.) (as assigned by Novartis to the investigative site) with a sequential subject number suffixed to it, so that each subject is numbered uniquely across the entire database.

Upon signing the informed consent form (ICF), the subject is assigned to the next sequential Subject No. available to the investigator through the Clinical Data Management System interface.

The investigator or designated staff will contact the Interactive Response Technology (IRT) and provide the requested identifying information to register the subject. Once assigned, the Subject No. must not be reused for any other subject and the Subject No. for that individual must not be changed. If the subject fails to be enrolled or randomized or start treatment for any reason, the reason will be entered into the appropriate eCRF page.

6.3.2 Treatment assignment, randomization

At visit C1D1, prior to dosing, all eligible subjects will be randomized via Interactive Response Technology (IRT) to one of the treatment arms. The investigator or his/her delegate will contact the IRT after confirming that the subject fulfills all the inclusion/exclusion criteria. The IRT will assign a randomization number to the subject, which will be used to link the subject to a treatment arm and will specify a unique medication number for the first package of study treatment to be dispensed to the subject.

The randomization numbers will be generated using the following procedure to ensure that treatment assignment is unbiased and concealed from subjects and investigator staff. A subject randomization list will be produced by the IRT provider using a validated system that automates the random assignment of subject numbers to randomization numbers. These randomization numbers are linked to the different treatment arms, which in turn are linked to medication numbers. A separate medication list will be produced by or under the responsibility of Novartis Global Clinical Supply (GCS) using a validated system that automates the random assignment of medication numbers to packs containing the study treatment.

Randomization will be stratified by histology (squamous vs non-squamous). Subjects with adenosquamous histology can be stratified as squamous or non-squamous based on the predominant histology.

The randomization scheme for subjects will be reviewed and approved by a member of the Randomization Office.

6.4 Treatment blinding

Treatment will be open to subjects, investigator staff, persons on site performing the assessments, and Novartis global and local trial teams. However, treatment will be blinded to the independant pathologists (evaluating the primary endpoint based on surgical resected sample) from time to randomization until database lock.

6.5 Dose escalation and dose modification

Investigational or other study treatment dose adjustments are not permitted.

6.5.1 Dose modifications

For subjects who do not tolerate the protocol-specified dosing schedule the following principles must be followed:

- For both canakinumab and pembrolizumab dose reductions are not permitted.

- Increase in the canakinumab dosing interval to Q6W is not applicable due to the short duration of the study.
- Canakinumab dose interruption for a maximum of 1 week is allowed as per [Table 6-2](#).
- Pembrolizumab will follow locally approved labels (if pembrolizumab is not yet approved in your country, refer to [Section 16.1](#)) and local clinical practice.

All dose changes in any study drugs must be recorded on the appropriate eCRF page.

6.5.1.1 Guidelines for mandatory dose modifications for canakinumab

Mandatory dose interruption or discontinuation of canakinumab in the management of adverse reactions are summarized in [Table 6-2](#). Clinical judgment of the treating physician should guide the management plan of each subject based on individual benefit/risk assessment. Canakinumab must be discontinued as listed for events in [Table 6-2](#). If a subject experiences more than one toxicity and there are conflicting recommendations between canakinumab and pembrolizumab dose modification, the most conservative dose modification should be followed.

In the combination arm, if one of the study drugs (canakinumab or pembrolizumab) is permanently discontinued because of unacceptable toxicity, per the investigator discretion, the other study drug (canakinumab or pembrolizumab) can continue alone in Cycle 2.

Table 6-2 Criteria for mandatory dose interruption and re-initiation for canakinumab due to adverse reactions

Worst toxicity (CTCAE v5.0) during a cycle of therapy	Mandatory dose schedule interruption and re-initiation for canakinumab ^g
General guidance for adverse events considered to be related to canakinumab (to be followed whenever no other specific guidance is described in this table)	
Grade 1/ Grade 2	Maintain canakinumab
Grade 3	Interrupt canakinumab until resolved to ≤ Grade 2, then: 
• If resolved in ≤ 7 days administer the second dose of canakinumab• If resolved in > 7 days discontinue canakinumab, due to the short study duration
Grade 4	Permanently discontinue canakinumab
Exceptions to the above general guidance^e	
Neutropenia (ANC)	
Grade 2 (ANC < 1500 - 1000/mm ³)	Interrupt canakinumab until resolved to ≤ Grade 1, then: 
• If resolved in ≤ 7 days, administer the second dose of canakinumab• If resolved in > 7 days discontinue canakinumab, due to the short study duration.
Grade 3 (ANC < 1000 - 500/mm ³)/ Grade 4 (ANC < 500/mm ³)	Permanently discontinue canakinumab

Worst toxicity (CTCAE v5.0) during a cycle of therapy	Mandatory dose schedule interruption and re-initiation for canakinumab^g
Febrile neutropenia	
• Grade 4	Permanently discontinue canakinumab
Thrombocytopenia	
Grade 3 (PLT < 50,000 - 25,000/mm ³)	Interrupt canakinumab until resolved to ≤ Grade 1, then: 
• If resolved in ≤ 7 days, administer the second dose of canakinumab• If resolved in > 7 days, permanently discontinue canakinumab
Serum creatinine	
Grade 3 (>3.0 x baseline; >3.0 - 6.0 x ULN)	Interrupt canakinumab until resolved to ≤ Grade 2 or baseline, then re-start at the same dose. 
• If resolved within 7 days, administer the second dose of canakinumab• If resolved in > 7 days discontinue canakinumab, due to the short study duration
Isolated total bilirubin elevation^a	
Grade 1 (Any elevation) > ULN – 1.5 x ULN	Fractionate bilirubin, evaluate for cholestatic liver injury (alkaline phosphatase (ALP)) or alternative causes of bilirubin elevation (e.g. disease progression [imaging]). Treat alternative causes according to local institutional guidelines. Maintain canakinumab
Grade 2 > 1.5 - 3.0 x ULN	Maintain canakinumab. Repeat Liver function tests (LFTs) within 48-72 hours, then monitor LFTs weekly until resolution to ≤ Grade 1 or to baseline.
Grade 3 > 3.0 - 10.0 x ULN ^b	Interrupt canakinumab. Repeat LFTs within 48-72 hours, then monitor LFTs weekly until resolution to ≤ Grade 1 or to baseline. 
• If resolved in ≤ 7 days, administer the second dose of canakinumab• If resolved in > 7 days, permanently discontinue canakinumab
Grade 4 > 10.0 x ULN ^b	see footnote* - otherwise discontinue canakinumab
Isolated AST or ALT elevation^a	
With normal baseline AST/ALT:	
Grade 1 > ULN - 3.0 x ULN	Maintain canakinumab
Grade 2 > 3.0 - 5.0 x ULN	Maintain canakinumab Repeat LFTs within 48-72 h; if still abnormal then monitor LFTs at least weekly, until resolved to ≤ 3.0 x ULN ^c

Worst toxicity (CTCAE v5.0) during a cycle of therapy	Mandatory dose schedule interruption and re-initiation for canakinumab^g
Grade 3: AST or ALT > 5.0 - 10.0 x ULN	
Interrupt canakinumab. Repeat LFTs within 48-72 h; monitor LFTs at least weekly, until resolved to \leq 3.0 x ULN. Then:
 
 • If resolved in \leq 7 days, administer the second dose of canakinumab • If resolved in > 7 days, discontinue canakinumab, due to the short study duration^c
Grade 3: AST or ALT > 10.0 - 20.0x ULN	Permanently discontinue canakinumab. Repeat LFTs within 48-72 h; monitor LFTs at least weekly until resolved to \leq baseline.
Grade 4: AST or ALT > 20.0 x ULN	Permanently discontinue canakinumab. Repeat LFTs within 48-72 h; monitor LFTs at least weekly until resolved to \leq baseline.
With abnormal baseline ALT/AST (up to Grade 1: \leq 3.0 ULN):	
ALT/AST > 2.0 x baseline AND > 5.0 x ULN	
Interrupt canakinumab. Repeat LFTs within 48-72 hours, then monitor LFTs weekly until recovery to baseline.
 
 • If resolved in \leq 7 days, administer the second dose of canakinumab • If resolved in > 7 days, discontinue canakinumab, due to the short study duration
ALT/AST > 3.0 x baseline AND >10 x ULN	Permanently discontinued canakinumab. Repeat LFTs within 48-72 hours, then monitor weekly until resolved to baseline.
AST/ALT increase associated with concomitant total bilirubin increase^a	
With normal baseline LFTs:	
AST or ALT >3.0 x ULN associated with concomitant TBIL >2.0 x ULN without evidence of cholestasis ^c (unless Gilbert syndrome)	
Interrupt canakinumab. Assess if case is true Drug Induced Liver Injury (DILI).*
 
If DILI confirmed - Permanently discontinue canakinumab
 
If Not DILI – interrupt canakinumab. Treat the identified cause according to institutional guidelines. Repeat LFTs within 48-72 hours, then monitor weekly, until enzyme levels resolve to \leq Grade 1 or Baseline^d
 
Refer to Section 6.5.2.1 for additional follow-up of potential DILI cases as applicable

With abnormal baseline LFTs:	

Worst toxicity (CTCAE v5.0) during a cycle of therapy	Mandatory dose schedule interruption and re-initiation for canakinumab^g
ALT or AST >3 x baseline OR ALT or AST >8 x ULN (whichever is lower) combined with TBIL >2.0 x ULN	After recovery, re-administration of the second dose of canakinumab could be considered only if Investigator assesses benefit to outweigh the risk. Any decision regarding re-administration of canakinumab and dose regimen, should be discussed with the Novartis medical and safety team. Refer to Section 6.5.2.1 for additional follow-up evaluations as applicable
Pancreatitis^f	
Grade 3	Interrupt canakinumab until resolved to ≤ Grade 1, then: 
 • If resolved in ≤ 7 days, administer the second dose of canakinumab • If resolved in > 7 days, discontinue canakinumab
Hypertension	
Grade 3	Interrupt canakinumab until resolved to ≤ Grade 1, then: 
 • If resolved in ≤ 7 days, administer the second dose of canakinumab • If resolved in > 7 days, discontinue canakinumab
Diarrhea - institute appropriate anti-diarrheal treatment and follow general guidelines	
Rash/photosensitivity - initiate/institute appropriate skin toxicity therapy (such as antihistamines and/or topical corticosteroids) and follow general guidelines	
Steven Johnson Syndrome, Toxic epidermal necrolysis	

 • Permanently discontinue canakinumab 	
Tuberculosis or reactivation of hepatitis	

 • Permanently discontinue canakinumab 	
Asymptomatic laboratory abnormalities - Provide supportive care and replacement therapy	

 • If clinically significant, follow general guidelines 	
LFTs – Liver Function Tests	
^a Refer to protocol Section 6.5.2.1 for monitoring of liver toxicity	
^b If TBIL > 3.0 x ULN is due to the indirect component only, and hemolysis as the etiology has been ruled out as per institutional guidelines continue canakinumab at the discretion of the investigator	
^c The subject should be monitored biweekly (including LFTs), or more frequently if clinically indicated, until TBIL have resolved to baseline or stabilization over 4 weeks	
^d Repeat within 48 hours then at least weekly until AST, ALT, or bilirubin have resolved to baseline or stabilization over 4 weeks	
^e If relatedness to canakinumab can be excluded with certainty and there is no risk for the patient, the dose interruption for canakinumab is not mandatory	
^f Note: A CT scan or other imaging study to assess the pancreas, liver, and gallbladder must be performed within 1 week of the first occurrence of any ≥ Grade 3 of amylase and/or lipase	

Worst toxicity (CTCAE v5.0) during a cycle of therapy	Mandatory dose schedule interruption and re-initiation for canakinumab^g

^g If AE is resolved prior to planned C2D1 dose interruption is not applicable. If AE is not resolved prior to planned C2D1, please follow dose interruption recommendation.
 
* An isolated bilirubin elevation is not typical for drug-induced liver injury. Bilirubin can be elevated either as part of a “Hy’s law” constellation with a preceding elevation of ALT/AST, or as part of a cholestatic reaction with simultaneous elevation of other cholestatic parameters (ALP, Gamma-glutamyl-transferase (GGT)). Isolated bilirubin can be seen in conjunction with drugs that inhibit bilirubin conjugation or excretion, but both scenarios do not typically represent liver injury.
 
Alternative causes of bilirubin elevation should therefore, be ruled out before basing dose modification decisions on bilirubin values alone.
	

6.5.2 Follow-up for toxicities

6.5.2.1 Follow up on potential drug-induced liver injury (DILI) cases

DILI Diagnosis

Subjects with transaminases increase combined with TBIL increase may be indicative of potentially severe DILI, and should be considered as clinically important events and should be assessed appropriately to establish diagnosis. The required clinical information, as detailed below, should be sought to obtain the medical diagnosis of the most likely cause of the observed laboratory abnormalities.

The threshold for potential DILI may depend on the subject’s baseline AST/ALT and TBIL value (Table 6-2, Section 6.5.1.1); subjects meeting any of the following criteria will require further follow-up as outlined below:

- For subjects with normal ALT and AST and TBIL value at baseline: AST or ALT $> 3.0 \times$ ULN combined with TBIL $> 2.0 \times$ ULN
- For subjects with elevated AST or ALT or TBIL value at baseline: AST or ALT $> 3.0 \times$ baseline or $8.0 \times$ ULN, whichever is lower combined with (TBIL $> 2.0 \times$ baseline AND $> 2.0 \times$ ULN)

As DILI is essentially a diagnosis of exclusion, other causes of abnormal liver tests should be considered and their role clarified before the diagnosis of DILI is confirmed.

Hepatic toxicity monitoring includes the following LFTs: albumin, ALT, AST, TBIL, direct and indirect bilirubin, ALP (fractionated if ALP is grade 2 or higher), creatine kinase, prothrombin time (PT) or INR and gamma-glutamyltransferase (GGT). For subjects with Gilbert Syndrome: total and direct bilirubin must be monitored, intensified monitoring applies to changes in direct bilirubin only.

Evaluate status of liver metastasis (new or exacerbation) or vascular occlusion – CT, MRI, duplex sonography.

Perform relevant examinations (Ultrasound or MRI, ERCP) as appropriate, to rule out if LFTs elevations are caused by cholestasis (defined as: ALP elevation $> 2.0 \times$ ULN with R value < 2 in subjects without bone metastasis, or elevation of ALP liver fraction in subjects with bone metastasis).

Note: The R value is calculated by dividing the ALT by the ALP, using multiples of the ULN for both values. It denotes the relative pattern of ALT and/or ALP elevation is due to cholestatic ($R \leq 2$), hepatocellular liver injury ($R \geq 5$), or mixed ($R > 2$ and < 5) liver injury.

Table 6-3 provides guidance on specific clinical and diagnostic assessments to be (OR which can be) performed to rule out possible alternative causes of the observed LFT abnormalities.

Table 6-3 Specific clinical and diagnostic assessments

Disease	Assessment
Hepatitis A, B, C, E	
IgM anti-Hepatitis A Virus (HAV); HBsAg, IgM & IgG anti-HBc, Hepatitis B Virus (HBV) DNA; anti-HCV, HCV RNA, IgM & IgG anti-HEV, HEV RNA
Cytomegalovirus (CMV), Herpes Simplex Virus (HSV), Epstein-Barr Virus (EBV) infection	
IgM & IgG anti-CMV, IgM & IgG anti-HSV; IgM & IgG anti-EBV
Autoimmune hepatitis	
Antinuclear Antibody (ANA) & Anti-Smooth Muscle Antibody (ASMA) titers, total IgM, IgG, IgE, IgA
Alcoholic hepatitis	
Ethanol history, GGT, Mean Corpuscular Volume (MCV), Carbohydrate Deficient-transferrin (CD-transferrin)
Nonalcoholic steatohepatitis	
Ultrasound or MRI
Hypoxic/ischemic hepatopathy	
Medical history: acute or chronic CHF, hypotension, hypoxia, hepatic venous occlusion. Ultrasound or MRI.
Biliary tract disease	
Ultrasound or MRI, ERCP as appropriate.
Wilson disease (if <40 yrs old)	
Caeruloplasmin
Hemochromatosis	
Ferritin, transferrin
Alpha-1-antitrypsin deficiency	
Alpha-1-antitrypsin

Other causes should also be considered based upon patients medical history (Hyperthyroidism / thyrotoxic hepatitis – T3, T4, Thyroid-Stimulating Hormone (TSH); Cardiovascular Disease (CVD) / Ischemic hepatitis – Electrocardiogram (ECG), prior hypotensive episodes; T1D / glycogenic hepatitis).

Following appropriate causality assessments, as outlined above, the causality of the drug is estimated as “probable” i.e. $>50\%$ likely, if it appears greater than all other causes combined. The term “drug-induced” indicates *probably caused* by the drug, not by something else, and only such a case can be considered DILI case and should be reported as an SAE.

DILI Management

In the absence of cholestasis, these subjects should be immediately discontinued from study drug treatment, and repeat LFT within 48 hours. The evaluation should include laboratory tests, detailed history, physical assessment, and the possibility of liver metastasis or new liver lesions, obstructions/compressions, etc.

Close observation is recommended in case of AST, ALT, and/or bilirubin increase requiring dose interruption, which involves:

- Repeating liver enzyme and serum bilirubin tests two or three times weekly. Frequency of re-testing can decrease to once a week or less if abnormalities stabilize or return to normal values.
- Obtaining a more detailed history of current symptoms.
- Obtaining a more detailed history of prior and/or concurrent diseases, including history of any pre-existing liver conditions or risk factors.
- Obtaining a history of concomitant drug use (including non-prescription medications, herbal and dietary supplements), alcohol use, recreational drug use, and special diets.
- Ruling out acute viral hepatitis types A, B, C, D, and E; hepatotropic virus infections (CMV, EBV, or HSV); autoimmune or alcoholic hepatitis; NASH; hypoxic/ischemic hepatopathy; and biliary tract disease.
- Obtaining a history of exposure to environmental chemical agents.
- Obtaining additional tests to evaluate liver function, as appropriate (e.g., INR, direct bilirubin).
- Considering gastroenterology or hepatology consultations.
- Assessing cardiovascular dysfunction or impaired liver oxygenation, including hypotension or right heart failure as possible etiologies for liver dysfunction.
- Obtaining a PK sample, as close as possible to last dose of study drug to determine exposure to study drug.
- Considering a liver biopsy, as clinically indicated to assess pathological change and degree of potential liver injury.

These assessments should be done in addition to the assessments of immunological markers and total bile acids described in [Section 8](#) .

All cases of DILI confirmed on repeat testing meeting the laboratory criteria defined above, with no other alternative cause for LFT abnormalities identified, should be considered as “medically significant” thus meeting the definition of SAE ([Section 10.1.2](#)) and must be reported as SAE using the term “potential drug-induced liver injury”. All events must be followed up with the outcome clearly documented. Results of tests as well as other clinically important information will be recorded in the eCRF.

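### For the same suspected liver-injury signal, Table 6-2 says interrupt canakinumab and assess, while Section 6.5.2.1 says discontinue study drug treatment at once

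*Protocol*

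**What the plan says.** Table 6-2 in Protocol Section 6.5.1.1 lists the mandatory interruption and re-initiation criteria for canakinumab. Its row for combined elevation with normal baseline liver tests is triggered by "AST or ALT >3.0 x ULN associated with concomitant TBIL >2.0 x ULN without evidence of cholestasis", with an exception for Gilbert syndrome. The action starts "Interrupt canakinumab. Assess if case is true Drug Induced Liver Injury (DILI". If DILI is confirmed, canakinumab is permanently discontinued. If not, it is interrupted, the cause is treated, and liver tests are repeated within 48-72 hours and then weekly. Footnote d, attached to that same cell, puts the repeat within 48 hours.

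The next row, for abnormal baseline liver tests, prints the sentence "After recovery, re-administration of the second dose of canakinumab could be considered only if Investigator assesses benefit to outweigh the risk" and requires discussion with the sponsor's medical and safety team.

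Section 6.5.2.1 defines potential DILI at normal baseline as "AST or ALT $> 3.0 \times$ ULN combined with TBIL $> 2.0 \times$ ULN". Under its DILI Management heading it says "In the absence of cholestasis, these subjects should be immediately discontinued from study drug treatment, and repeat LFT within 48 hours".

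**The concern.** A site that meets this signal after the first dose finds two instructions that refer to each other. One holds canakinumab and makes permanent discontinuation depend on the outcome of the causality work-up. The other takes the subject off study drug treatment before that work-up is done. Two sites could each follow the protocol and reach different answers on whether the second dose remains possible.

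The reporting would differ too. SAP Section 2.4.1 summarises interruptions and permanent discontinuations separately, and SAP Section 2.7.1 does the same for adverse events leading to each. The same clinical event could therefore land in different tables according to which passage the site had read.

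**Working it through.** No arithmetic underlies the point, so the check is a comparison of the texts for the normal-baseline signal.

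| | Table 6-2 | Section 6.5.2.1 |
|---|---|---|
| Trigger | AST/ALT > 3 x ULN, TBIL > 2 x ULN, no cholestasis | Same thresholds; action applies without cholestasis |
| First action | Interrupt, then assess for true DILI | Discontinue immediately |
| Permanent stop | Only if DILI is confirmed | At once |
| Drugs covered | Canakinumab | Study drug treatment |
| First retest | 48-72 h (cell); within 48 h (footnote d) | Within 48 h |

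**Are these the same subjects?** Yes. The thresholds are identical. Section 6.5.2.1 cites Table 6-2 for them, and the table sends the reader to Section 6.5.2.1 for follow-up of potential cases.

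**Suspected or confirmed cases?** Section 6.5.2.1 says that "other causes of abnormal liver tests should be considered and their role clarified before the diagnosis of DILI is confirmed". The discontinuation order depends on absence of cholestasis, which is a rule-out condition. It is followed by a repeat test and by further work-up: "The evaluation should include laboratory tests, detailed history, physical assessment, and the possibility of liver metastasis or new liver lesions". An instruction issued while other causes are still being sought fits suspected cases better than confirmed ones.

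**Does discontinued mean held?** The glossary defines study treatment discontinuation as a permanent stop before the planned completion date. Table 6-2 itself separates the terms: the drug is interrupted first, and discontinued if resolution takes more than 7 days.

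**Is there a tie-break?** Section 6.5.1.1 has a most-conservative rule, but it covers conflicts between canakinumab and pembrolizumab modifications, not conflicts between Table 6-2 and Section 6.5.2.1.

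**Abnormal baseline.** Both places use ALT/AST > 3 x baseline or > 8 x ULN, whichever is lower. For bilirubin, Section 6.5.2.1 requires > 2 x baseline and > 2 x ULN; Table 6-2 requires only > 2 x ULN. The first condition implies the second. A subject with abnormal baseline ALT or AST who meets the Section 6.5.2.1 trigger therefore also meets the Table 6-2 trigger and, without cholestasis, falls under both the order to discontinue and the sentence on re-administration.

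**Where dosing can differ.** Two doses are planned, on Days 1 and 22 (Table 6-4). After the second, no dose remains to withhold. After the first, confirmed DILI ends canakinumab under both texts. That leaves signals later judged not to be DILI. Footnote g makes interruption inapplicable if the event resolves before the planned second dose, and Section 6.5.1 limits interruption to 1 week. Within that subset the difference is at most 1 of 2 doses (1/2 = 50% of the planned regimen).

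**Retest.** A test at exactly 48 hours satisfies both wordings. One at 60 hours meets the table cell but neither footnote d nor Section 6.5.2.1.

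**The case against.** The best reply is that the texts can be read consistently. The sentence just before the DILI Management heading describes what may be called a DILI case. If the subjects in the next sentence are those cases, Section 6.5.2.1 agrees with the table's rule for confirmed DILI. The following paragraph of Section 6.5.2.1 covers elevations that require dose interruption, so the section itself recognises interruption with work-up. The structure also points to Table 6-2 as the dosing text: Section 6.5.1.1 ties mandatory discontinuation to the table, Section 8 refers to Section 6.5.1 for dose modification, and Section 6.5.2 is headed as follow-up.

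This shows that the conflict rests on a reading and is not a flat contradiction. It does not remove it. The confirmed-case reading sits badly with a repeat test and a search for other causes after the order, and nothing expressly gives the table precedence. The confirmed-case reading also leaves the retest mismatch in place, including the one within Table 6-2.

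A reader might infer that Table 6-2 expressly permits re-dosing for the normal-baseline signal. The available text does not support this: the re-administration sentence is printed in the abnormal-baseline row, which carries no cholestasis condition, and whether the original cell spanned both rows cannot be told. A reader might also infer that sites would manage the signal in opposite ways. They would not: both texts stop canakinumab at once, and both end in discontinuation of canakinumab if DILI is confirmed.

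**Conclusion.** The inconsistency stands for the normal-baseline signal, on the assumption that Section 6.5.2.1 addresses suspected cases. The retest discrepancy stands without that assumption. The texts also differ in scope: Section 6.5.2.1 stops study drug treatment, while Table 6-2 deals with canakinumab, and Section 6.5.1.1 lets the other drug continue alone in Cycle 2 when one is permanently discontinued for toxicity.

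The size is limited. It is tempting to apply the problem to every subject with combined elevations, but whether the second dose may be given can differ only for signals after dose 1 later judged not to be DILI. The other effects are on retest timing and on the interruption and discontinuation counts. The documents give no basis for estimating how many subjects are involved.

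It is also tempting to carry the problem through to the primary analysis, because discontinuation is a named intercurrent event. The documents do not support that. Protocol Section 12.4.2 and SAP Section 2.5.2 handle it by treatment policy, so the label changes whether the event is recorded but not how the subject's MPR is classified.

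**What to change.** Reconcile Table 6-2, both the cell and footnote d, with Section 6.5.2.1. Each liver-test scenario should carry one action, one statement of which drugs it covers, one condition for any re-dosing and one retest interval. State whether the DILI Management instruction applies to suspected or confirmed cases, and which baseline rows the re-administration sentence covers. One passage should then refer to the other instead of restating it. The sponsor's clinical team must decide which version stands; this review takes no view on that.

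The cost is wording, in an amendment or an investigator notification. SAP Section 1 records that recruitment was halted on 1 February 2022. If dosing is already complete, the remaining action is to document which instruction was applied to any affected subject, so that the interruption and discontinuation tables can be read correctly.
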